**Table 14: RSV Season Surveillance Procedures**

RSV Season Surveillance (November 1 through March 31 following inoculation)	
Clinical Tasks	
 
• Obtain interim history
 
• Review safety data
 
• Document findings
 

Follow-up Preparation	
 
• Continue with weekly contacts through March 31
 
• Schedule an Illness Visit if warranted
 
• Schedule the Post-RSV Season Study Visit (targeted April 1st - April 30th with allowable window through September 30th)
 

### 6.6.3 Post-RSV Season Surveillance Study Visit

The Post-RSV Season Surveillance Visit will occur in the calendar year following receipt of study product, ideally between April 1st and April 30th through September 30th.

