# 1 BACKGROUND AND SCIENTIFIC RATIONALE

## 1.1 BACKGROUND

### 1.1.1 Epidemiology, Disease Burden, and the Need for a Vaccine

In the United States alone, RSV is responsible for 75,000 to 125,000 hospitalizations of infants yearly (1), and worldwide, RSV infects at least 34 million children under 5 years old, resulting in an estimated 3.4 million RSV LRI hospitalizations and 66,000 to 199,000 RSV-attributable deaths each year (2). In temperate climates, annual RSV epidemics occur in late winter and early spring, and nearly all children are infected within the first 2 years of life. RSV illness can range from mild upper respiratory tract illness (URI), including rhinitis, pharyngitis, and coryza, to severe LRI, including bronchiolitis and pneumonia. Beyond the acute burden of disease caused by RSV, severe RSV disease in infancy may predispose to reactive airway disease during childhood (3, 4).

RSV is an enveloped RNA virus that is a member of the newly organized *Pneumoviridae* family, genus *Orthopneumovirus* (5). RSV has a single negative-sense strand RNA genome of 15.2 kilobases encoding 10 mRNAs. Each mRNA encodes a single protein, with the exception of the M2 mRNA, which contains 2 overlapping ORFs. The 11 RSV proteins are the viral RNA-binding nucleoprotein N, the phosphoprotein P, the large polymerase protein L, the attachment glycoprotein G, the fusion glycoprotein F, the small hydrophobic surface glycoprotein SH, the internal matrix protein M, the 2 nonstructural proteins NS1 and NS2, and the M2-1 and M2-2 proteins encoded by the M2 mRNA. The gene order is: 3'-NS1-NS2-N-P-M-SH-G-F-M2-L-5'. RSV transcription and genome replication take place exclusively in the cytoplasm, and virions form by budding from the apical plasma membrane of respiratory epithelial cells.

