**Table 15: Post-RSV Seasonal Surveillance Study Visit Procedures**

Post-RSV Season Study Visit	
Administrative Tasks	

Provide second study compensation

Clinical Tasks	

Document findings related to study procedures

Laboratory Tasks	Blood Collect blood for: 

Serum antibodies to RSV

	Nasosorption SAM Strip Collect nasosorption strip for: 

RSV antibody assays

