### **6.10.3 Immunologic Assays**

For measurement of RSV serum antibodies, serum specimens will be obtained in RSV-seropositive children not more than 56 days prior to inoculation and on Day 28 (+7) postinoculation; and in RSV-seronegative infants and children not more than 42 days prior to inoculation and on Day 56 (+7) postinoculation. In addition, pre-first RSV season and post-first RSV season serum specimens will be collected in all RSV-seronegative infants and children. These samples will be used to determine whether a four-fold or greater rise in antibody titer has occurred during the first RSV season, which would signify infection with wt RSV. This will allow comparison of the rate and severity of significant RSV illness following infection with wt virus, as well as comparison of the antibody responses, in vaccine and placebo recipients.

For subjects in group 2 enrolled in surveillance during the second RSV season, RSV neutralizing antibodies will also be measured in serum specimens collected before and after the second RSV season: between October 1 and October 31 (pre-season 2), and with a target window of April 1 to April 30 which can be extended through September 30 (post-season 2). This will allow assessment of the duration of antibody responses to vaccination, and comparison of the rate and severity of significant RSV illness following infection with wt virus in vaccine and placebo recipients during the second season.

Specimens will be obtained by venipuncture, finger-stick, or heel-stick. No more than 5 mL of blood will be drawn at each blood draw visit. A maximum of 10 mL of blood will be taken from RSV-seropositive subjects for study purposes. A maximum of 20 mL of blood will be taken from RSV-seronegative subjects for study purposes from screening through season 1 surveillance. A maximum of an additional 10 mL of blood will be taken from RSV-seronegative subjects who participate in season 2 surveillance.

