Post-RSV Season	Ideally April 1 to April 30; allowable through Sept 30th in the year after the inoculation	
 
• Grade <math>\geq 3</math> AEs or SAEs that are deemed related to Post-RSV Season Study Visit procedures
 
	
 
• All medications related to the recorded event
 

Throughout study	ANY	
 
• Unresolved AEs or SAEs with onset from Day 0 to midnight on the 28th day after inoculation
 
• Unresolved SAEs with onset prior to the 56th day following inoculation
 
• Unresolved SAEs with onset during RSV Surveillance Period or related to the Pre- or Post-RSV Season Study Visit
 
	
 
• All medications related to the recorded event
 

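### Post-season serum may be drawn up to September 30 while illness capture stops on March 31, so a post-season infection can count as seasonal with its illness uncollected

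*Combined protocol and SAP*

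**What the plan says.** **Infection.** Section 6.10.3 uses the pre- and post-season sera to establish whether "a four-fold or greater rise in antibody titer has occurred during the first RSV season, which would signify infection with wt RSV". The stated purpose includes "comparison of the rate and severity of significant RSV illness following infection with wt virus" in vaccine and placebo recipients.

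**Timing of the second serum.** Section 6.6.3 sets it "ideally between April 1st and April 30th through September 30th". Tables 14, 20 and 32 give the same April target and September 30 limit. Section 6.10.3 repeats the extension for season 2, and Section 6.7 otherwise carries the season 1 procedures over.

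**Illness capture.** Section 6.6.2 runs surveillance from November 1 to March 31, and Table 14 says "Continue with weekly contacts through March 31". Table 20 records medically attended fever, URI, LRI and otitis media for those dates only.

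**Post-season visit.** The single clinical task in Table 15 is "Document findings related to study procedures". Table 32 marks interim history for weekly contacts, illness visits and early discontinuation, but not for this visit. In the Post-RSV Season row of Table 20, new CRF entries are limited to Grade 3 or higher AEs, or SAEs, "that are deemed related to Post-RSV Season Study Visit procedures".

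**Analysis.** Sections 9.2.2 and 9.5.2 summarise the frequency and severity of medically attended respiratory and febrile illness among group 2 children with natural infection in the season. They give no rule by draw date.

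**The concern.** The two parts of the secondary summary cover different calendar periods. The infected set can include anyone whose titer rose at any time up to the draw, while illness is collected only up to March 31. A child infected in, say, May and bled in August has a rise that the serum pair cannot date. If that child is classed as infected during the season, illness from that infection is absent by design, because no contact, illness visit or history covers it.

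This bears on the first secondary objective (Section 2.2), which describes illness after wild-type infection in vaccine and placebo recipients. Section 1.1.1 recalls disease enhancement after the formalin-inactivated vaccine, so the description has some safety meaning. Group 2 has only 21 to 30 children and the infected subset will be smaller still, so one or two misplaced children can visibly change a proportion. If attendance dates differed by arm, the between-arm reading would be affected as well.

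**Working it through.** The plan states no precision or power for this objective, so there is no figure to reproduce. The check compares calendar windows and then illustrates the effect under stated assumptions.

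**1. Windows.** Inputs: pre-season serum October 1-31 (Table 13), illness capture November 1 to March 31 (Section 6.6.2), post-season serum April 1 to September 30 (Section 6.6.3). In a non-leap year, capture lasts 30 + 31 + 31 + 28 + 31 = 151 days.

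Length of the serum interval = days from the pre-season draw to October 31 + 151 + days from March 31 to the post-season draw. Coverage = 151 / length.

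| Pre-season draw | Post-season draw | Length (days) | Coverage | Uncovered after March 31 |
|---|---|---|---|---|
| Oct 31 | Apr 1 | 0 + 151 + 1 = 152 | 99% | 1 |
| Oct 31 | Apr 30 | 0 + 151 + 30 = 181 | 83% | 30 |
| Oct 1 | Apr 30 | 30 + 151 + 30 = 211 | 72% | 30 |
| Oct 31 | Sep 30 | 0 + 151 + 183 = 334 | 45% | 183 |
| Oct 1 | Sep 30 | 30 + 151 + 183 = 364 | 41% | 183 |

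A child whose Day 56 visit falls on or after October 1 uses that serum as the pre-season sample (Section 6.6.1), so the interval may start later. The last column does not change. An early October draw leaves a smaller gap of the same kind before the season, up to 30 days.

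**2. How many children could be affected.** The documents give no risk of infection between April and September, so the per-child risk q is assumed. Chance of at least one such rise among n children = 1 − (1 − q)^n, taking every child as drawn at the end of the window. That is an upper-bound scenario, because the target is April.

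| Assumed q | n = 30 (all group 2) | n = 10 (placebo) |
|---|---|---|
| 1% | 26% | 10% |
| 2% | 45% | 18% |
| 5% | 79% | 40% |
| 10% | 96% | 65% |

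**3. Effect on the summary, with assumed counts.** Suppose 6 children are infected in season and 3 have a recorded illness: 3/6 = 50%.

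- One post-season rise with no recorded illness: 3/7 = 43%.
- Two such rises: 3/8 = 38%.
- One post-season rise in a child who also had an unrelated medically attended cold in January: (3 + 1)/(6 + 1) = 57%.

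The last line matters because Sections 9.2.2 and 9.5.2 do not require the illness itself to be RSV-positive. Illness due to the post-season infection is always lost, but the summary as worded can move either way.

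**The case against.** Four arguments carry weight.

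- **Little virus may circulate then.** Section 3 confines enrollment to April 1 through October 31 to avoid the usual circulation period, and Section 6.6.2 bases the surveillance dates on local Baltimore data. Against this, Section 1.1.1 says that "annual RSV epidemics occur in late winter and early spring". That is a general remark about temperate climates. It makes some April infections plausible but does not support appreciable risk through to September. This argument stands as a limit on size.
- **183 days is the edge of a visit tolerance.** It is a length of time, not an infection risk or a bias. Children seen in the target month have at most 30 uncovered days. This stands.
- **Direction.** A reader might infer that illness per infection must be understated. That does not follow for the summary as worded, because any medically attended respiratory or febrile illness from November to March can enter it. The tendency to understate holds for RSV-attributable illness.
- **Classification.** A reader might also infer that the plan orders every late rise to be counted as seasonal. It does not say so. Sections 9.2.2 and 9.5.2 speak of infection during the season, and Section 9.5.1 leaves detail to the statistical analysis plan. What can be said is that no rule for late sera appears in the combined document, and that the sera alone cannot date a rise.

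The objective is also descriptive: Section 9.1.2 calls the study exploratory, and Section 9.5.1 plans no formal between-arm test on this outcome. Section 9.5.2 plans individual titer listings, which would let single cases be examined, but it does not ask for draw dates. None of these arguments supplies the missing illness history.

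**Conclusion.** The mismatch is real in the current text. Seasonal infection is read from a serum that may be drawn up to September 30, while illness is collected only to March 31 and the post-season visit does not ask about it. For children drawn after March 31, and mainly those drawn well after April, an infection after the season can be counted as seasonal with its illness uncollected. The summary of illness among infected children may therefore be distorted in either season, and RSV-attributable illness per infection would tend to be understated.

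The size cannot be estimated from the documents. It depends on how many children are drawn late and on RSV circulation after March, and neither is given. If April-October circulation is as low as Section 3 presumes, the effect is probably small. The probabilities and proportions in the working rest on assumed risks and counts and are illustrations only. The documents do not support reading this as a demonstrated bias of known direction in the planned summary. It is a modest gap in a descriptive secondary objective, worth closing because closing it costs little.

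**What to change.** 1. Add to Tables 15 and 32, and to the Post-RSV Season row of Table 20, an interim history of medically attended fever, URI, otitis media and LRI from April 1 to the date of the post-season draw, recorded on the CRF. Apply it in both seasons.
2. In Section 9.5.2, include the draw date in the listing of pre- and post-season titers.
3. In Section 9.5.2, keep all sera in the main summary and add a sensitivity summary restricted to children whose post-season serum was drawn April 1-30.

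The April restriction should not become the main rule, even with RSV-positive surveillance washes accepted as an alternative. Those washes are triggered by medically attended illness. Among late-drawn children, such a rule would keep infections that led to care and drop in-season infections that did not, which inflates illness per infection. An April cut-off may also miss late infections: the protocol reads the vaccine response in seronegative children at Day 56, and 56 days after March 15 is May 10. The wild-type response may of course follow a different course.

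Cost: one history item per child at an existing visit and one extra descriptive row, with no added visit or blood draw. Illness reported by history after March 31 will lack a nasal wash to confirm RSV, so it should be shown as unconfirmed. The smaller October gap remains.

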**Table 15: Post-RSV Seasonal Surveillance Study Visit Procedures**

Post-RSV Season Study Visit	
Administrative Tasks	

Provide second study compensation

Clinical Tasks	

Document findings related to study procedures

Laboratory Tasks	Blood Collect blood for: 

Serum antibodies to RSV

	Nasosorption SAM Strip Collect nasosorption strip for: 

RSV antibody assays

### 6.7 RSV SURVEILLANCE: SECOND SEASON

The second RSV seasonal surveillance is November 1 through March 31 in the second season following inoculation and will be optional for RSV-seronegative children (group 2) who have participated in the first surveillance season. An ICD for the second season of RSV surveillance must be signed before any procedures are performed. If a participant's parent/guardian agrees to have their child participate in a second season of RSV surveillance, the procedures for the second season will be identical to those outlined for the first season in Section 6.6, except that a Pre-Season 2 Visit with blood and nasal sample will always be required, and the Post-Season 2 Visit will occur in the second calendar year following enrollment in the study.

### 6.8 ILLNESS VISIT

The timeframe after staff notification in which the Illness Visit must occur depends on the study phase and the grading of the fever and respiratory symptoms per Section 8.2 and If the Illness Visit occurs on a day concurrent with an in-person study visit, a single nasal wash collection is required and adventitious agent testing will be requested. All symptoms will be followed until resolution or deemed stable or chronic by appropriate medical personnel (e.g., medical doctor or nurse practitioner). Illness Visits may occur during any of the study phases.

If the acute or post-acute phases overlap the surveillance period (between November 1 and March 31), then the timelines for the acute and post-acute phases will be used.

**Table 16: Illness Visit Timeframe**

Illness Visit Timeframe			
Phase	Symptoms	Grade	Visit Timeframe
Acute	Fever, otitis media or URI	1	Within 3 days
Acute	Fever, otitis media or URI	$\geq 2$	Within 2 days
Acute	LRI	Any	Within 1 day
Post-Acute	SAE that meets study pause or stop criteria (Section 8.3)	$\geq 2$	Within 3 days
RSV Season Surveillance	Medically attended fever, otitis media, URI or LRI	$\geq 2$	Within 3 days

**Table 17: Illness Visit Procedures**

Illness Visit Procedures			
Administrative Tasks		
 
• Complete Adventitious Agent Assay Request for rRT-PCR on nasal wash for adventitious agents
 
	
Clinical Tasks		
 
• Obtain and document from parent/guardian the participant's interim history including: 
 
▪ medications and/or immunizations
 
▪ signs and symptoms of illness
 
▪ highest temperature reading, indicate temperature method
 
 
 
• Perform focused clinical examination
 
• Address any concerns
 
• Review safety data
 
• Document findings
 
	
Laboratory Tasks	Nasal Wash	Collect nasal wash for: 
 
• Viral detection and quantification
 
	
Follow-up Preparation		
 
• Schedule follow-up as appropriate
 
	

## 6.9 EARLY DISCONTINUATION STUDY VISIT

In the event that a child is unable to continue participation in the study, parent/guardian will be encouraged to allow the participant to complete safety monitoring through Day 28 for RSV-seropositive participants and through Day 56 for RSV-seronegative participants. Every effort should be made to schedule a final Early Discontinuation Visit.

**Table 18: Early Discontinuation Procedures**

Early Discontinuation	
Administrative Tasks	
 
• Record data on CRF
 

Clinical Tasks	
 
• Obtain interim history
 
• Address any concerns
 
• Review safety data
 
• Encourage parent/guardian to allow the participant to complete safety monitoring through Day 28 for RSV-seropositive participants and through Day 56 for RSV-seronegative participants
 
• Document findings
 

Laboratory Tasks	
Blood
 
Collect blood for:
 
 
• Serum antibodies to RSV
 
 
Nasal Wash and/or Nasosorption SAM Strip
 
If Early Discontinuation Visit is within 28 days of inoculation for RSV-seropositive participants or 56 days for RSV-seronegative participants (Appendix II), collect nasal wash for:
 
 
• Viral detection and quantification
 
• RSV antibody assays
 
 
Collect nasosorption strip for:
 
 
• RSV antibody assays
 
 
Note: The nasosorption must be performed prior to the nasal wash.

## 6.10 LABORATORY PROCEDURES

### 6.10.1 Specimen Collection

Specimens will be collected for this study as indicated in the Schedule of Events. Further information on collection of blood and nasal wash specimens will also be provided in the MOP.

### 6.10.2 Virus Detection

Specimens for viral culture and quantification of vaccine virus shedding will be obtained by nasal wash with approximately 20 mL of Ringer's lactate solution once before and approximately 6 times after inoculation for RSV-seropositive participants and approximately 8 times after inoculation RSV-seronegative participants as shown in [Appendix II](#). These specimens may also be tested for adventitious respiratory viruses if needed. Additional nasal wash specimens for detection of RSV and adventitious respiratory viruses by culture and rRT-PCR will also be obtained from participants who meet illness criteria during the initial phase (Day 0 through Day 28 for RSV-seropositive participants; Day 0 through Day 56 for RSV-seronegative participants) as well as during the RSV First Seasonal Surveillance Period (November 1 – March 31) for all RSV-seronegative participants and the RSV Second Season Surveillance for RSV-seronegative participants whose parents/guardians elect to participate. If a participant becomes ill during the Acute or Post-Acute Phase, then up to 10 additional nasal washes over a 28-day period for group 1 participants and over a 56-day period for group 2 participants may be obtained to exclude infection with an adventitious virus. Laboratory testing will be performed by personnel who are not involved with clinical assessment to maintain the blinding status.

### **6.10.3 Immunologic Assays**

For measurement of RSV serum antibodies, serum specimens will be obtained in RSV-seropositive children not more than 56 days prior to inoculation and on Day 28 (+7) postinoculation; and in RSV-seronegative infants and children not more than 42 days prior to inoculation and on Day 56 (+7) postinoculation. In addition, pre-first RSV season and post-first RSV season serum specimens will be collected in all RSV-seronegative infants and children. These samples will be used to determine whether a four-fold or greater rise in antibody titer has occurred during the first RSV season, which would signify infection with wt RSV. This will allow comparison of the rate and severity of significant RSV illness following infection with wt virus, as well as comparison of the antibody responses, in vaccine and placebo recipients.

For subjects in group 2 enrolled in surveillance during the second RSV season, RSV neutralizing antibodies will also be measured in serum specimens collected before and after the second RSV season: between October 1 and October 31 (pre-season 2), and with a target window of April 1 to April 30 which can be extended through September 30 (post-season 2). This will allow assessment of the duration of antibody responses to vaccination, and comparison of the rate and severity of significant RSV illness following infection with wt virus in vaccine and placebo recipients during the second season.

Specimens will be obtained by venipuncture, finger-stick, or heel-stick. No more than 5 mL of blood will be drawn at each blood draw visit. A maximum of 10 mL of blood will be taken from RSV-seropositive subjects for study purposes. A maximum of 20 mL of blood will be taken from RSV-seronegative subjects for study purposes from screening through season 1 surveillance. A maximum of an additional 10 mL of blood will be taken from RSV-seronegative subjects who participate in season 2 surveillance.

For RSV-seropositive participants, nasal wash specimens and/or nasosorption strips for measurement of secretory immunity will be obtained before inoculation and 28 days after inoculation. For RSV-seronegative participants, nasal wash specimens and/or nasosorption strips for measurement of secretory immunity will be obtained before inoculation, 28 and 56 days after inoculation, and at the pre- and post-RSV season 1 surveillance visits. These specimens may be generated from the same nasal wash obtained for viral culture, but specimen processing is different as described in the MOP. If the parent/guardian opts to participate in the second year of RSV surveillance, a nasal wash specimen and/or nasosorption strip will also be obtained at the second year pre- and post-RSV surveillance visits to measure secretory immunity.

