**Table 20: AE CRF Recording Requirements for RSV-Seronegative Subjects**

Study Phase at the Time of Event Onset	Calendar Date	AEs to Record on CRFs	Concomitant Medications to Record on CRFs
Day 0 through midnight of 28 th day following inoculation (Acute Phase)	ANY	
 
• All SAEs
 
• All solicited AEs that meet Appendix IV criteria
 
• All unsolicited AEs (Grades 1 to 4), with the exception of the following conditions if not treated with prescription medication or non-prescription medications with antipyretic properties: diaper rashes, teething pain, and spitting up
 
	
Record these medications on the CRFs regardless of whether the related event is recorded on the CRFs:
 
 
• All cough and cold remedies including decongestants, cough suppressants, expectorants
 
• All nasal sprays (except saline spray)
 
• All antihistamines
 
• All antipyretics
 
• All prescription medications
 
 
For SAEs and LRIs:
 
 
• All medications related to the recorded event
 

From the 29 th day after inoculation to the 56 th day after inoculation (Post-Acute Phase)	ANY	
 
• All SAEs
 
	
 
• All medications related to the recorded event
 

From Day 56 Visit through start of RSV Season Surveillance Period	Up to October 31 in year of inoculation	
 
• Grade <math>\geq 3</math> AEs or SAEs that is deemed related to Pre-RSV Season Study Visit procedures
 
	
 
• All medications related to the recorded event
 

RSV First and Second Season Surveillance Periods	November 1 to March 31	
 
• Fevers, LRIs, URIs, and/or otitis media that are medically attended
 
• All SAEs
 
 
Note: These events do not need to meet the Appendix IV criteria
	
For SAEs and LRIs (all grades):
 
 
• All medications related to the recorded event
 
 
Medications related to recorded medically attended illness should be documented in source notes

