## 9.2.2 Secondary Outcome Measures

- The frequency and severity of symptomatic, medically attended respiratory and febrile illness in the RSV-seronegative (group 2) vaccine and placebo recipients who experience natural infection with wt RSV during the first RSV season and through the second RSV season for group 2 subjects who participate in a second RSV season surveillance.
- The antibody responses in the RSV-seronegative vaccine and placebo recipients who experience natural infection with wt RSV during the first RSV season and during a second RSV season for those who choose to participate.
- The quality and epitope specificity of RSF F-specific antibody

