### **9.5.2 Assessment of Secondary Objectives**

The summary of the frequency and severity of symptomatic, medically attended respiratory and febrile illness in the RSV-seronegative vaccine and placebo recipients who experience natural infection with wt RSV during the first RSV season will be presented. A summary will also be presented of the frequency and severity of symptomatic, medically attended respiratory and febrile illness in the RSV-seronegative vaccine and placebo recipients who participate in a second RSV season surveillance and who experience natural infection with wt RSV during the second RSV season. In addition, a line listing of the individual RSV antibody titer pre- and post-First RSV Season Surveillance Period will be prepared, as well as a listing of the RSV antibody titer pre- and post-Second RSV Season Surveillance Period for those seronegative subjects who participate in the second RSV season surveillance. In addition, the geometric mean and median antibody titers will be provided, for each treatment group. The adaptive immune responses to vaccine will be summarized for each treatment group. A line listing of the mucosal antibody response detected in nasal wash specimens will be prepared.

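### Season illness is summarised only among Group 2 children with natural RSV infection, a post-randomisation subset whose only stated marker the vaccine can shift

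*Combined protocol and SAP*

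**What the plan says.** Secondary objective 1 (Section 2.2), the outcome measure (9.2.2) and the analysis (9.5.2) all describe medically attended respiratory and febrile illness in the same subset. In 9.2.2 it is Group 2 children "who experience natural infection with wt RSV during the first RSV season". In 9.5.2 the illness summary for "vaccine and placebo recipients who experience natural infection with wt RSV during the first RSV season will be presented". The second-season summary covers those "who participate in a second RSV season surveillance and who experience natural infection with wt RSV during the second RSV season".

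Section 9 does not say how natural infection is recognised. The only criterion tied to a season is in 6.10.3, which gives the purpose of the pre- and post-season sera: "determine whether a four-fold or greater rise in antibody titer has occurred during the first RSV season, which would signify infection with wt RSV". The same section continues: "This will allow comparison of the rate and severity of significant RSV illness following infection with wt virus", in vaccine and placebo recipients.

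The data collected are wider than this summary. Table 20 records "Fevers, LRIs, URIs, and/or otitis media that are medically attended" for Group 2 children during the surveillance periods, whether or not infection is established. Section 6.10.2 adds: "Additional nasal wash specimens for detection of RSV and adventitious respiratory viruses by culture and rRT-PCR will also be obtained" when illness criteria are met, including in the surveillance seasons. No section says that an RSV-positive wash counts as natural infection, and 9.5.2 lists no illness summary over all Group 2 children.

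**The concern.** The denominator is formed after randomisation by an event that the vaccine may change, so the two infected groups need not be comparable even though the arms were randomised. The stated marker adds a second difficulty: it is a rise from a baseline that the vaccine is meant to raise. If an infection takes a primed and an unprimed child to the same titer, the primed child shows the smaller rise and is less likely to be counted.

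Two conclusions are at stake. Severity per infected vaccinee could look too high, in a programme where enhanced disease is the historical safety concern (1.1.1). Conversely, infections could be undercounted in vaccinees, which looks like protection. A true reduction in infection or in illness per child is not shown directly. With at most 20 vaccinees and 10 placebo recipients, a few children entering or leaving the subset change the message.

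**Working it through.** **The plan's own figures.** The documents give no attack rate, illness rate or power for season illness. Table 26 (one-sided Fisher exact test, alpha 0.05, 20 vs 10) concerns response proportions. Exact enumeration gives 80.6%, 79.7%, 79.5%, 80.1% and 79.7% for its five rows, so it reproduces, and this point does not touch it.

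**Inputs from the documents.** 20 vaccinees and 10 placebo recipients if 30 are enrolled (9.3.1). Seronegative means below 1:40, that is 2^5.3 (Section 3). Four-fold is 2 log2 units. The predecessor vaccine gave neutralizing responses in 53% of recipients at 10^5 PFU and 80% at 10^6 PFU, and this candidate is expected to be more immunogenic (1.2.1.1). Many vaccinees should therefore start the season with a raised titer.

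**Assumed, because the documents are silent.** Post-infection log2 titer with mean m and a given SD; attack rate 50% (range 30% to 70%); q = 40% medically attended illness given infection; s1 and s0 = chance of a four-fold rise in infected children with and without such illness.

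**Step 1: entry to the subset.** P(four-fold rise) = 1 − Φ((pre + 2 − m)/SD), with SD 1:

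| Pre-season titer | m = 8 | m = 9 | m = 10 |
|---|---|---|---|
| 2^5.3 (1:40) | 0.76 | 0.96 | 1.00 |
| 2^6 | 0.50 | 0.84 | 0.98 |
| 2^7 | 0.16 | 0.50 | 0.84 |
| 2^8 | 0.02 | 0.16 | 0.50 |

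With SD 1.5 the m = 9 column reads 0.87, 0.75, 0.50, 0.25. In every column a higher baseline lowers the chance of entry. How far depends on m, and on both arms sharing one m. If infection boosted vaccinees higher, the gap could close: 0.84 (2^7, m = 10) against 0.76 (2^5.3, m = 8).

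**Step 2: a vaccine with no effect on infection or illness.** Share ill among entrants = q·s1 / (q·s1 + (1 − q)·s0). Entrants = n × attack rate × (q·s1 + (1 − q)·s0). At a 50% attack rate:

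| Arm and pattern | s1 / s0 | Entrants | Ill among entrants |
|---|---|---|---|
| Placebo | 0.9 / 0.9 | 10 × 0.5 × 0.90 = 4.5 | 40% |
| Vaccine, mild infections missed | 0.9 / 0.5 | 20 × 0.5 × 0.66 = 6.6 | 0.36/0.66 = 55% |
| Vaccine, all missed more, mild most | 0.7 / 0.4 | 20 × 0.5 × 0.52 = 5.2 | 0.28/0.52 = 54% |
| Vaccine, missed regardless of illness | 0.6 / 0.6 | 20 × 0.5 × 0.60 = 6.0 | 40% |
| Vaccine, ill children missed | 0.5 / 0.9 | 20 × 0.5 × 0.74 = 7.4 | 0.20/0.74 = 27% |

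At placebo sensitivity, 20 × 0.5 × 0.9 = 9.0 vaccinees would enter, so every vaccine pattern undercounts infections. The share ill does not depend on the attack rate. Over 30% to 70%, entrants number about 3 to 10 vaccinees and 3 to 6 placebo recipients.

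**Step 3: a vaccine that works.** If it halves infection and leaves illness given infection at 40%, illness per child is 0.25 × 0.4 = 10% against 0.50 × 0.4 = 20%. The infected-only figure is 40% in both arms, even with perfect detection of infection. If instead it halves illness given infection (20% against 40%) and s1 = 0.9, the infected-only figure in vaccinees is 20%, 27%, 36% and 43% as s0 falls through 0.9, 0.6, 0.4 and 0.3.

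**Step 4: does counting positive washes settle it?** Suppose every RSV illness is confirmed by wash, so s1 = 1 in both arms, with s0 = 0.5 in vaccinees and 0.9 in placebo recipients. For the no-effect vaccine the figures are 0.40/(0.40 + 0.30) = 57% and 0.40/(0.40 + 0.54) = 43%. No ill child is lost, but the gap remains, because infections without illness still rest on serology. Over all children the figure is 0.5 × 0.4 = 20% in both arms.

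**The case against.** Sections 9.2.2 and 9.5.2 mention no titer. The four-fold sentence sits under assay methods and says what a rise would signify, not that infection requires one. Illness washes are tested for RSV in the season, and on a plain reading a child with wild-type RSV in a wash has had natural infection. This stands to the extent that a reader who infers a serology-only entry rule goes beyond the text. What remains is that the definition is unwritten, and Step 4 shows that the broader definition alone does not make the infected groups comparable.

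Conditioning on infection follows secondary objective 1, and severity after wild-type infection is a natural way to look for enhanced disease. This also stands, and is why the infected-only table should stay.

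A reader might infer that any prevention would be invisible. The documents do not support that. Frequency is part of the outcome, 6.10.3 speaks of the rate of illness, individual season titers are listed, and counts could be set against known arm sizes. The information is collected; the plan does not commit to the summary that would show it.

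Finally, the trial is exploratory, season illness is secondary, and 9.5.1 confines formal testing to other endpoints. This stands and limits the weight of the point.

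**Conclusion.** The point holds as a weakness in a secondary, descriptive summary that should be corrected. The planned comparison rests on a subset the vaccine may change, its defining event is not fully specified, and no summary over all Group 2 children is listed. No primary test, alpha level or sample size is affected.

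Two stronger readings go too far. One is that severity in vaccinees is biased upward. It can be, if missed rises fall mainly on mild infections (55% against 40% under the assumptions above). It is undistorted if missed rises are unrelated to illness, and it would run downward if ill children were the ones missed. The documents do not say which applies. The other is that half or more of infections in responders would be missed. From 1:128 the chance of a four-fold rise is 0.16, 0.50 or 0.84 for assumed post-infection means of 2^8, 2^9 or 2^10 (SD 1), and the documents give no season titer from which to choose. The evidence in Section 3 that children with titers of 1:40 or more respond poorly concerns live vaccine virus, not wild-type RSV, so it is supportive only.

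**What to change.** In 9.2.2 and 9.5.2:

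1. Define natural infection as wild-type RSV detected by culture or rRT-PCR in an illness wash and/or a four-fold or greater titer rise. Require the virus to be confirmed as wild-type, since 6.6.2 allows surveillance to overlap the Acute Phase, when vaccine virus may be shed. Fix the definition before unblinded review; 6.3 allows the code to be released to clinical staff once a block completes acute monitoring, so this should be done early.
2. Add a summary by arm of the number and severity of medically attended illnesses with confirmed wild-type RSV, over all inoculated Group 2 children under surveillance. Give exact 90% confidence intervals per arm and no formal test. For the second season, use all children who opted in.
3. Keep the infected-only severity table, labelled as conditional on infection and descriptive.

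The cost is wording and one extra table from data already planned. The downside is wide intervals: Table 25 gives 2% to 28% for 10% of 20 children and 4% to 51% for 20% of 10.
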